## **Safety Considerations**

Participants randomized to continuing LT4 treatment will continue to face side effects associated with chronic LT4 use, usually side effects indicative of excessive dosage (exogenous hyperthyroidism). Such effects include flushing, sweating, weight loss, tremor, restlessness, excitability, insomnia, angina pain, cardiac arrhythmias, palpitations, tachycardia, diarrhea, muscle cramps, muscle weakness, menstrual irregularities, and heat intolerance. Although, we do not anticipate any side-effects of continuing LT4 for participants who were already taking it as part of their usual care, at the baseline visit we will exclude participants with thyroid function test results suggestive of exogenous hyperthyroidism. We will also exclude patients who were not previously adherent to their LT4 treatment. This is a safety measure to avoid the possibility of developing exogenous hyperthyroidism for a patient who had normal thyroid labs at the baseline visit as a result of not receiving consistent LT4 therapy previously. All participants will have thyroid function tests 6-8 weeks after their initial visit, which is the recommended time to assess the effects of LT4 changes, and at 6 months post-randomization. If hyperthyroidism is confirmed, participants will be required to stop the trial medication and will be referred to their clinicians for treatment.

As with any medication, allergic reactions are a possibility. Allergy to LT4 is extremely rare and very unlikely to occur in patients who have been taking this medication chronically. Participants will have already been taking LT4 prior to enrollment in the study. If assigned to the LT4 group, the participant will continue the pre-study dose of LT4 throughout the study. Participants will be advised to notify the PI or research coordinator if they experience a significant rash, wheezing or other allergy symptoms.

LT4 interacts with the following drugs: anticoagulants, anti-convulsants, anti-arrhythmics, antidiabetics, beta-blockers, antidepressants, sympathomimetics, cardiac glycosides, antineoplastics, nonsteroidal anti-inflammatory drugs, sex hormones, lipid regulating drugs, and general anesthetics. However, it should be noted that interactions are generally weak and have very limited clinical relevance for the treatment of SCH with LT4. If Veterans' LT4-prescribers have concerns about their participation in the RCT, they will be invited to contact the PI.

The risks involved with discontinuation of LT4 (participants allocated to placebo) include development or worsening of hypothyroidism-related symptoms such as weight gain, fatigue, cold intolerance, body aches, muscle weakness, edema, depression, constipation, hair loss, dry skin, brittle nails, menstrual abnormalities, neck pain/discomfort, memory trouble and cognition issues. In patients with SCH, these clinical manifestations are usually mild. However, given the evidence that LT4 therapy does not confer important hypothyroid-symptom-related benefits for patients with SCH, it is unlikely that the participants who discontinue LT4 will experience the onset or worsening of hypothyroidism-related symptoms. Participants will be informed of this risk and the array of hypothyroidism-related symptoms. We will be monitoring for these side effects during the clinic visits and monthly phone calls and participants will be instructed to notify the PI or research coordinator if they experience these symptoms. Participants may return to the medication they were using before the study, at any time and for any reason. The PI will also discontinue study medication if ongoing treatment becomes inappropriate for the participant.

Fluctuating thyroid hormone levels may be harmful to a fetus. Because of this risk, women who are pregnant or plan to become pregnant are not eligible to take part in this study. We will ask women of child-bearing potential to use birth control for the duration of the study. Acceptable methods of birth control are: (1) hormonal methods, such as birth control pills, patches, injections, vaginal ring, or implants, (2) barrier methods, such as a condom or diaphragm, used with spermicide (a foam, cream, or gel that kills sperm), (3) intrauterine devices, and (4) abstinence (no sex). Women will be instructed to

notify the study team immediately if they miss a period or think they might be pregnant during the study. The PI may ask for permission to collect information about the outcome of the pregnancy.

There is a physical risk from blood collection. We plan to collect blood for research purposes three times during the study. We may collect additional blood, if needed, for safety assessment or repeat lab. The amount of blood collected will not exceed 17 mL per study collection. Possible risks of a blood draw include pain, bruising and/or infection, nausea, dizziness, and syncope. Both discomfort and bruising should disappear in a few days. The blood sample will be collected in the CAVHS Outpatient Lab in accordance with best practices to minimize any risks of possible adverse events. All personnel involved in the testing of blood samples will follow all needed safety and data security protocols. The risk associated with the blood collection for research purposes is not greater than the usual risk associated with standard of care.

There is a psychological risk that may be associated with the collection of quality-of-life information from RCT participants. The Veterans may be unaware of the extent to which they are experiencing symptoms, such as depression or memory loss. However, the study questions are similar to those encountered in clinical care and we have sought to use only the necessary measures that would have relevance for the participants. The questionnaires are self-administered, and the participants can skip questions that make them uncomfortable.

The clinical trial will be double blinded. Participant blinding to treatment allocation will be ensured through use of matched capsules for LT4 and placebo. However, when participants complete the clinical trial, they will be informed of whether they were allocated to LT4 or placebo and will be advised to discuss this with their usual (non-study) clinicians. In addition, there will be immediate response to requests for unblinding from clinicians if needed for optimal clinical care. A CPRS Research Note will have been written by the research coordinator describing the study procedures and listing emergency contact information. In the event that unblinding is needed for optimal clinical care, an attempt will be made to maintain blinding of the research team.

Full details of all adverse events of special interest (new atrial fibrillation, fractures, acute myocardial infarction, stroke, acute coronary syndrome, heart failure, mortality) including the nature of the event, relationship to study drug and outcome will be recorded. Adverse events of special interest will be monitored and followed up until satisfactory resolution or stabilization. All adverse events will be assessed for seriousness. Serious adverse events will also be assessed for causality, expectedness, and severity. This assessment will be carried out by the PI or designated Investigator. If the study demonstrates a convincing pattern of serious adverse events with either LT4 or placebo (LT4 discontinuation), this would be an important endpoint in its own right. If an association of adverse events is noted with either LT4 or placebo allocation, this would require careful consideration as to whether it is ethical and appropriate to continue with the trial. Adverse events will be recorded at all visits and telephone contacts. Participants will be informed of potential adverse events and advised to contact the study team if needed. Adverse events, adverse drug reactions, unexpected adverse reactions, serious adverse reactions, or suspected unexpected serious adverse events will be recorded, notified, assessed, reported, analyzed, and managed in accordance with the Medicines for Human Use (Clinical Trials) Regulations. The PI may withdraw patients from the study and refer them to their clinicians, who would be notified of the participant's study withdrawal, in the event of inter-current illness or adverse events.

A safety monitor will be designated for the project. They will be a CAVHS provider with medical knowledge and training sufficient to enable review of adverse events and identify any safety concerns for the project. A log documenting all adverse events, including hypothyroidism and hyperthyroidism at Month 2, will be maintained on the secure S drive behind the VA firewall by the SC. The safety monitor

will review the log at pre-specified timepoints (at least monthly). They will be blinded to the study medication assignment.

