**Randomized Clinical Trial (RCT) protocol**  
**5/30/2023**

**Principal Investigator (PI):**  
**[name], MS**

**NCT 04288115**

**Aim. Evaluate the feasibility of LT4 discontinuation among Veterans with SCH and determine the changes in quality-of-life measures, treatment burden, and adverse events.**

Design: Double-blind, placebo-controlled randomized clinical trial

Performance site: CAVHS

Participants: Fifty veterans with LT4-treated SCH will be randomized to either (1) continue current dose of LT4 [pre-study dose] or (2) placebo. Up to 150 veterans will need to sign consent and HIPAA authorization to reach 50 randomized participants due to the anticipated screen failure rate. The screen failure rate accounts for participants whose baseline lab results (TSH, FT4 and LDL) are out of study range. Participants will be identified from CDW/Strategic Management (Aim 1) and referrals from CAVHS providers (including Primary Care or Endocrine clinic providers).

Exclusion Criteria: (1) TSH > 10 mIU/L (at any point), (2) LT4 dose more than 75 mcg daily, (3) use of antithyroid medications, amiodarone, tyrosine kinase inhibitors or lithium, (4) history of thyroidectomy or radioactive iodine therapy, (5) LT4 suppressive therapy for thyroid cancer, goiter or inflammation, (6) pregnancy or plans for pregnancy in the next 6 months, (7) an unstable medical condition that would jeopardize safety or interfere with study participation, (8) hospitalization for major illness within the previous 4 weeks, (9) severe hypothyroidism-related symptoms, (10) strong family history of hypothyroidism, (11) severe dyslipidemia, (12) acute coronary artery syndrome, acute myocarditis, or pancarditis or stroke within the previous 12 months, (13) Grade IV New York Heart Association (NYHA) heart failure, (14) receiving services from hospice, (15) lack of decision-making capacity, (16) terminal medical condition for which life expectancy would be less than 6 months, (17) not willing to stop LT4, (18) self-reported non-adherence to LT4 therapy and (19) abnormal TSH at time of screening for participation (assessed during Baseline Visit). Pregnancy testing will be performed for females of child-bearing potential that sign consent to participate in the study. The results will be reviewed prior to randomization.

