Recruitment: We will send an **IRB-approved opt-out letter** to eligible veterans identified from CDW/Strategic Management or referral from CAVHS provider. The Principal Investigator (PI) has presented the study background, goals, and procedures to endocrinologists and primary care clinicians at CAVHS, answered questions, and got feedback from them (Development phase). A post-presentation poll of primary care physicians showed that 75% felt that LT4 discontinuation was acceptable in patients with SCH and 97% were comfortable with randomization of their eligible patients in the study. All endocrinologists felt that LT4 discontinuation was acceptable in patients with SCH and were comfortable with randomization of their eligible patients in the study. Clinicians were informed that Veterans under their care may be invited to participate and that those Veterans may want to discuss participation with their clinicians prior to enrolling. Before beginning to recruit, we will repeat the presentation to CAVHS clinicians who might prescribe LT4, including primary care, medicine, and endocrinology service clinicians, to refresh their memories and ensure that we reach clinicians new to CAVHS. In addition, an email with materials describing the study will be sent to clinicians who miss the presentation. Clinicians will be invited to contact the PI if they have questions or concerns about the study. The PI will utilize the Medicine and Primary Care quarterly conference to update clinicians. Study staff will send up to 100 IRB-approved opt-out letters weekly until all eligible veterans identified are sent the letter or 50 veterans are randomized (whichever occurs first). The pool of potential participants will be identified from CDW/Strategic Management and referrals from CAVHS providers. Women and minorities will be included in the study in proportion to their presence among CAVHS patients. We will submit and get approval for a **telephone script**. The designated study staff will call potential participants, with varying lengths of LT4 therapy, that do not opt-out (after at least two weeks from the mail date of the opt-out letter) and use the IRB-approved telephone script to guide the conversation.

Consenting: Written ICF and HIPAA will be obtained by the designated study staff prior to any study activities.

Intervention: (1) Continue current dose of LT4 [control or “sham discontinuation”] or (2) placebo [intervention or “real discontinuation”]

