medication to dispose of any unused study medication in the manner in which they usually dispose of expired medications or offer to have them return the unused study medication to CAVHS. Participants may withdraw from the study at any time. Withdrawal by the participant will be defined as any participant that informs the study team that they do not wish to continue the study medication, do not wish to allow any further collection of data, and do not wish to have any further contact with the study team. If they do so, they will be considered withdrawn voluntarily from the study. We will document the circumstance(s) and reason(s) for participant withdrawal. The PI may also withdraw participants from the study. This may occur in the event of inter-current illness, adverse events, protocol violations, non-compliance, or administrative reasons. We will assist the participant to ensure that appropriate medication is started at the time of withdrawal. We will instruct participants who withdraw (or are withdrawn) from the study to dispose of any unused study medication in the manner in which they usually dispose of expired medications or offer to have them return the unused study medication to CAVHS. Participants withdrawn from the study will not be replaced. To avoid breaking the blind, results of Visit 1 (Month 2) laboratory tests will not be published in CPRS but will be recorded in the Veterans Information Systems and Technology Architecture (VISTA), which is not used by clinicians for lab review. These lab results will be reviewed by Unblinded Personnel.

**Randomization Lab Criteria:** Baseline lab results (TSH, FT4 and lipid profile) will be reviewed prior to randomization by the Investigator or SC. To qualify for randomization, TSH and FT4 must be within normal reference range and LDL must be  $\leq 190$  mg/dL. Normal reference range for TSH: 0.54 – 5.6 mIU/mL. Normal reference range for FT4: 0.47 – 1.41 ng/dL.

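### Entry sets no minimum time since LT4 was started or its dose last changed, so a Veteran can be randomized on baseline labs that the plan's own 6-8 week interval treats as too early to read

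*Combined protocol and SAP*

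**What the plan says.** Safety Considerations places the first on-study thyroid tests "6-8 weeks after their initial visit, which is the recommended time to assess the effects of LT4 changes". The same paragraph explains why non-adherent patients are kept out: the worry is "a patient who had normal thyroid labs at the baseline visit as a result of not receiving consistent LT4 therapy previously", who might then become hyperthyroid once LT4 is taken regularly.

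The entry rules are these:

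- **Exclusion Criteria.** There are 19 items. The only limit on current LT4 exposure is the dose cap, "LT4 dose more than 75 mcg daily". Prior adherence is screened as "self-reported non-adherence to LT4 therapy".
- **Randomization Lab Criteria.** "To qualify for randomization, TSH and FT4 must be within normal reference range", and LDL must be at most 190 mg/dL. No repeat test is required.
- **Recruitment.** Veterans to be telephoned are described as people "with varying lengths of LT4 therapy".
- **Data Collected.** Duration of LT4 therapy is listed at Clinic Follow-up 2 (Month 6). The Baseline Visit list has medical history but does not name LT4 duration. Time since the last dose change is listed nowhere.

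Controls stay on their pre-study dose throughout. Planned Analysis uses change from baseline to 6 months, with baseline measures as ANCOVA covariates.

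**The concern.** The plan's reason for excluding non-adherent patients is that a normal baseline result may not show what the full dose does when taken steadily. A dose started or altered shortly before baseline raises the same problem, but nothing at entry addresses it.

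Three things are at stake. The lab gate may pass people whose thyroid status is still moving. Their baseline ThyPRO scores, lipids and weight, which serve as covariates and as the start of each change score, may not reflect the settled state on that dose. Some controls may also meet a stopping limit at Month 2 with no change of treatment in the trial. In the placebo arm there is a question of interpretation as well: stopping LT4 begun a few weeks earlier is not the same as stopping established treatment.

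**Working it through.** The plan gives no figure for this point, so the check is mainly of the text.

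**1. Does any entry rule impose the interval?** None of the 19 exclusions mentions time on LT4 or time since a dose change. The lab criteria concern values only. References in Safety Considerations to chronic LT4 use are descriptive and are not criteria. Recruitment imposes some delay, because calls start at least two weeks after the opt-out letter. A Veteran already on LT4 when identified has thus been on it for more than two weeks, but that is short of 6-8 weeks and places no limit on dose changes.

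**2. Timing for a dose changed two weeks before randomization (an example).** Allowing little time between the baseline sample and randomization:

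- Baseline sample: about 2 weeks after the change, short of the 6-8 weeks named.
- Clinic Follow-up 1, at 6-8 weeks: 2 + 6 = 8 to 2 + 8 = 10 weeks. This is the first result that the plan's own interval would call interpretable.
- Month 6, about 26 weeks: 2 + 26 = 28 weeks, which is 28/8 = 3.5 times the longer end of the interval.

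The gap therefore bears on baseline and Month 2, and much less on Month 6 values.

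**3. Entry limits against stopping limits.**

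| Test | To be randomized | Study medication stopped |
|---|---|---|
| TSH | 0.54 to 5.6 | below 0.34 or above 10 |
| FT4 | 0.47 to 1.41 | below 0.47 or above 1.41 |

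TSH has room on both sides: 0.54 − 0.34 = 0.20 below and 10 − 5.6 = 4.4 above. FT4 has none. Its numbers are identical, although the units are printed as ng/dL for entry and ng/mL for stopping. A control who entered near an FT4 limit while still moving could cross it by Month 2.

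**4. What a Month 2 lab stop does.** Under Study Medication Discontinuation Criteria the study coordinator is unblinded when overt hypothyroidism or hyperthyroidism is notified, and results go to the participant. The Safety Monitor section has the coordinator keep the adverse event log, which includes these events. Each stop thus ends assigned treatment, adds a logged event and unblinds the person who keeps the log. One stop in an arm of 50/2 = 25 is 1/25 = 4 percentage points. This is a unit of count, not a forecast that any stop will occur.

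**5. Could it move the ThyPRO test?** The documents give no share of recent changers and no drift, so what follows is sensitivity only. Inputs from the plan are 25 per arm, SD 20, margin 14 and one-sided α 0.05. The standard error is 20 × √(2/25) = 5.66, df = 48, and the critical t is 1.677. With a true harm of 14 points, the chance of wrongly declaring non-inferiority is P(T > 1.677), where T is noncentral t with noncentrality (shift in control mean)/5.66. A positive shift means that controls worsen.

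| Assumed drift in controls | Shift | False non-inferiority |
|---|---|---|
| none | 0 | 5.0% |
| 5% worsen by 5 points | +0.25 | 5.5% |
| 10% worsen by 10 points | +1.0 | 7.1% |
| 20% worsen by 15 points | +3.0 | 13.1% |
| 10% improve by 10 points | −1.0 | 3.4% |
| 20% improve by 15 points | −3.0 | 1.5% |

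The answer runs from 1.5% to 13.1% according to an assumed sign and size, neither of which the documents supply.

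**The case against.** The strongest reply is that this hardly touches the comparison. Recent changers fall in both arms on average, and the tested scores are taken at 6 months, when a control still on study medication has been on a fixed dose for about that long. The ThyPRO test is secondary in a pilot whose primary outcome is feasibility. The dose cap, monthly contact and Month 2 labs add safety cover. Most of this stands. It limits the bias argument, but it does not make the baseline labs interpretable, and the Month 2 labs act only after randomization. Randomization also does not equalize what follows: controls continue towards the new steady state while placebo recipients stop. With 50 participants, chance imbalance is possible.

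A reader might infer more than the documents support:

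- **That the gap biases the trial towards non-inferiority.** This needs controls to worsen on Hypothyroid Symptoms and Tiredness. A recent start or increase could equally leave them still improving, which works the other way. The hazard that Safety Considerations names is exogenous hyperthyroidism, and tiredness is not among the effects it lists for excess LT4.
- **That any control leaving the reference range is stopped.** For TSH this is wrong, as the limits above show. Only the FT4 limits coincide.
- **That the plan sets out to enrol recent starters.** The wording on varying lengths of therapy permits them; no sentence seeks them. A broad range of durations may also be a deliberate choice of population.
- **That pharmacy-fill data with an 80% cut-off should replace self-report.** The documents do not say that the data warehouse holds fills, and the 80-100% rule in Compliance and Withdrawal describes reported use of study medication, not use before entry.

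**Conclusion.** The point holds as a gap in eligibility and baseline data. The plan states an interval for judging LT4 changes and guards against misleading normal labs in one situation, but lets the same problem through when a dose is new or recently altered. It also does not list the data at baseline that would show who is affected, so a sensitivity analysis is not assured.

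The consequences that the documents support are a less reliable lab gate, baseline values that may not be settled, and possible avoidable Month 2 stops in controls, chiefly through FT4, at 4 percentage points of the arm for each stop and with the coordinator unblinded each time. How many participants would be affected is unknown.

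For the Month 6 ThyPRO comparison, neither size nor direction can be estimated, and the likeliest result is added noise. The conclusion rests on reading the plan's silence as permission, which the recruitment wording supports. It does not rest on any of the error rates above. The change is worth making because it follows from the plan's own reasoning and costs little.

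**What to change.** 1. In Exclusion Criteria and Randomization Lab Criteria, require the pre-study LT4 dose to have been unchanged before the baseline blood sample for the interval that Safety Considerations itself names. Defer recent changers until it has passed rather than excluding them, and align the Recruitment wording.
2. Add LT4 duration and time since last dose change to the Baseline Visit list in Data Collected.
3. Reconcile Safety Considerations, which excludes previously non-adherent patients without qualification, with the exclusion list, which acts only on self-report. Either say how adherence is checked beyond self-report, or state that self-report is the check and acknowledge the limit.
4. Reconcile the printed FT4 units between the randomization and discontinuation criteria.

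The cost is one eligibility line, two baseline items and a record check by existing staff. The downside is that a few candidates are deferred by some weeks, which slightly slows recruitment, itself part of the primary feasibility outcome.

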and pulse. Analysis of covariance (ANCOVA) models will be employed to analyze these outcomes. Baseline measures and gender will be included in the models as covariates. A one-sided t-test will be used to determine whether the mean ThyPRO Hypothyroid Symptoms and Tiredness scores for the real discontinuation group differ from the mean ThyPRO Hypothyroid Symptoms and Tiredness scores of the sham discontinuation group by no more than 14 points. An  $\alpha$ -level of 0.05 will be used to determine the statistical significance of the non-inferiority test for each ThyPRO domain. Failure to reject the null hypothesis will suggest that the QoL measures in the real discontinuation group, on average, are more than 14 points worse than in the sham discontinuation group. This will be considered as evidence against our conjecture that discontinuation does not negatively affect the QoL of patients with SCH. In addition, analyses comparing groups with respect to adverse event rates will be performed using chi-square tests. Analyses will be based on the intention-to-treat principle. Statistical analyses will be done using SAS 9.4 (SAS Institute, Cary, NC).

*Additional details Analysis Plan:* We will add a Biostatistician to the project. They will be hired through an IPA to work on the project. The Biostatistician will be sent the data set by encrypted email and will use computer software on their laptop (non-VA) to complete the analysis. No name, date of birth or SSN will be included in the data set for analysis. Those data points will remain within the VA protected environment.

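### Symptom-level monitoring is named only for the harms of stopping LT4, so the comparison of adverse event rates may lean against discontinuation

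*Combined protocol and SAP*

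**What the plan says.** Safety Considerations treats the two directions of harm differently.

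- **Stopping LT4 (placebo arm).** Fifteen hypothyroid-type symptoms are listed. Participants are told about them ("Participants will be informed of this risk and the array of hypothyroidism-related symptoms"), staff look for them, and participants are asked to report them: "We will be monitoring for these side effects during the clinic visits and monthly phone calls and participants will be instructed to notify the PI".
- **Continuing LT4 (control arm).** Sixteen effects of excess dosage are listed ("Such effects include flushing, sweating, weight loss, tremor, restlessness, excitability, insomnia, angina pain, cardiac arrhythmias, palpitations, tachycardia, diarrhea, muscle cramps, muscle weakness", and two more). No sentence says that these symptoms will be monitored at visits or calls. The one specific reporting instruction concerns allergy: "Participants will be advised to notify the PI or research coordinator if they experience a significant rash, wheezing or other allergy symptoms". The section also states that "we do not anticipate any side-effects of continuing LT4 for participants who were already taking it as part of their usual care".

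Other provisions apply to both arms. Safety Considerations requires thyroid tests ("All participants will have thyroid function tests 6-8 weeks after their initial visit", and again at 6 months). It also names adverse events of special interest, such as new atrial fibrillation and fractures, says that adverse events are recorded at every visit and call, and says that participants hear about potential adverse events in general. The Data Collected paragraph has pulse and weight measured at the clinic visits. The monitoring plan under Data Management has general health and side effects assessed at calls and visits.

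The Planned Analysis then states that "analyses comparing groups with respect to adverse event rates will be performed using chi-square tests". It does not define which events or categories enter those rates.

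**The concern.** Adverse events are part of the trial's stated Aim. Symptoms that are named and looked for tend to be recorded more often than symptoms left to a general question. Here each arm's expected harm sits on a different list, and only one list has named monitoring. Blinding makes the questions the same in both arms. It does not make capture equal for two kinds of symptom when the questions name only one kind.

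The plan could then report more adverse events after discontinuation when true harm is equal, or understate a drop in LT4-type symptoms after stopping. Two uses of the data would be affected. Safety Considerations says that an association of adverse events with either allocation would prompt a review of whether the trial should go on. The sample size paragraph says that the pilot is meant to inform a full-scale trial.

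**Working it through.** **1. Compare the two lists.** The LT4-excess list has 16 items and the hypothyroid list has 15. Muscle weakness and menstrual changes are on both, so 16 − 2 = 14 LT4-excess items fall outside the named monitoring.

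**2. Credit what else covers those 14.** Weight loss and tachycardia can be picked up by measured weight and pulse. Arrhythmia and angina are partly covered by the special-interest events (new atrial fibrillation, acute coronary syndrome). That leaves 14 − 4 = 10 with no specific route beyond general assessment: insomnia, tremor, heat intolerance, sweating, flushing, palpitations, diarrhea, restlessness, excitability and muscle cramps. Thyroid tests detect biochemical excess but do not record these symptoms.

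**3. When does unequal capture create a gap?** The documents give no adverse event rate, capture rate or power for this comparison, so there is no stated figure to reproduce. Everything in this step except the sample size is assumed. Take 25 per arm (50 randomized 1:1). Let *e* be the true rate of arm-specific symptoms, equal in both arms; *b* a background rate of monitored symptoms; and *r* the share of LT4-type symptoms captured, with monitored symptoms fully captured.

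- Placebo: P = 1 − (1 − b)(1 − e)
- LT4: P = 1 − (1 − b)(1 − e·r)
- False gap = (1 − b)·e·(1 − r)

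The gap is zero if e = 0 (no arm-specific symptoms) or r = 1 (full capture). For example, with b = 0.20, e = 0.10 and r = 0.50, the gap is 0.80 × 0.10 × 0.50 = 0.04.

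The last two columns give results for r = 0.75 / 0.50 / 0.25. Rejection is the exact probability that the uncorrected chi-square test is significant at 0.05; the value with equal capture (r = 1) is in brackets.

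| b | e | False gap (points) | Rejection |
|---|---|---|---|
| 0.20 | 0.05 | 1 / 2 / 3 | 5.5 / 5.8 / 6.2% (5.4%) |
| 0.20 | 0.10 | 2 / 4 / 6 | 5.7 / 6.6 / 8.3% (5.4%) |
| 0.20 | 0.30 | 6 / 12 / 18 | 8.5 / 15.7 / 28.3% (6.3%) |
| 0 | 0.30 | 7.5 / 15 / 22.5 | 9.7 / 25.7 / 57.3% (5.4%) |

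**4. A second set of assumptions.** Give both symptom types a background of 10 to 20% in both arms, capture 90% of monitored symptoms, and capture 60% or 30% of LT4-type symptoms. With no excess in either arm, the reported difference is 0 at any capture rate. If each arm has a true excess of its own harm of 10 points, the reported gap against placebo is 3 or 6 points. With a 20-point excess it is 6 or 12 points.

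**5. Is there an adverse event assessment at every contact?** The Data Collected paragraph lists one at Clinic Follow-up 1 and at all four telephone visits, but not at Clinic Follow-up 2 (Month 6). Safety Considerations says all visits and telephone contacts. The two must be reconciled, or a checklist tied to the listed assessments would miss the final visit.

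**The case against.** The strongest reply is that the contacts are blinded and identical, so the test stays valid unless LT4-type symptoms really differ between arms. The protocol gives reasons to expect little difference. Control participants keep their pre-study dose, thyroid tests must be normal before randomization, self-reported non-adherence is an exclusion, and no side effects of continuing are anticipated. Exposure changes only in the placebo arm, so it is natural to name the symptoms of that change. Under a rule that counts only new or worsened symptoms, long-standing symptoms on an unchanged dose would not count at all. All of this stands, and it makes the low-rate rows of the table more plausible than the high-rate ones.

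It is also fair that the monitoring sentence sits in a risk narrative and describes no checklist. The visit forms are separate source documents that are not in the reviewed text, and neither is the consent form. A balanced form cannot be ruled out, but nothing in the protocol requires one.

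A reader might infer that LT4-type harms go unmonitored, or that 14 of 16 are simply missed. The documents do not support that: tests, pulse, weight, special-interest events and general assessment cover part of the list, and hyperthyroidism is logged beside hypothyroidism. What remains is narrower: minor LT4-type symptoms depend on general questions, while minor hypothyroid symptoms are looked for by name.

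**Conclusion.** The asymmetry in the text is real, and its effect is a risk. A reader might conclude that the adverse event comparison is biased against discontinuation. That is not shown, because it requires both a true difference in LT4-type symptoms between arms and under-capture of those symptoms, and the documents establish neither.

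The size cannot be estimated from the documents. Under low assumed rates (5 to 10% arm-specific, 20% background) the false gap is 1 to 6 points and the test's rejection rate barely moves. The 57% rejection rate needs 30% arm-specific symptoms, no background, and 100% against 25% capture, so it should not be quoted as an expected effect. Adverse events are not the primary outcome of this feasibility pilot. The point is a cheap improvement to make; it does not undermine the trial.

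**What to change.** - **Data Collected and Safety Considerations:** use one fixed symptom checklist that combines the LT4-excess and hypothyroid lists. Ask it in the same words of every participant at baseline, at every telephone visit and at both clinic follow-ups. Reconcile the Clinic Follow-up 2 entry with the statement that adverse events are recorded at all visits, so that Month 6 is included.
- **Reporting instruction in Safety Considerations:** give participants in both arms the same combined list of what to report, alongside the allergy instruction.
- **Planned Analysis:** define the adverse event categories for the chi-square tests. Count only symptoms that are new or worse than at baseline. Report solicited events by arm, split into LT4-excess type and hypothyroid type, separately from spontaneously reported events. The baseline record also allows symptoms that resolve to be tabulated.

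The cost is wording in three places and one source-document form, a few minutes per contact, and a higher count of minor events. No extra visits, staff or participants are needed.
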